Familial Hypercholesterolemia	
DO NOT include the following:	DO NOT include the following:
Low HDL	Pulmonary hypertension
	Intracranial hypertension
	Venous hypertension
	Pre-eclampsia or Maternal Hypertension
	Portal hypertension
	Ocular hypertension

Randomization: Prior to study start, [name] will develop a 1:1 blocked randomization scheme, stratified by site. This randomization scheme will be carried out using the randomization module in RedCap. Participants will be randomized by RedCap at the time of their baseline visit to avoid randomizing participants who have not yet completed consent.

Education control group: Participants assigned to the education group will receive usual care enhanced with general prevention education delivered by the prevention nurse. This active comparator is appropriate because participants have multiple risk factors for ASCVD, and advisory committees for prior studies have recommended this for similar study populations. The prevention educational modules will be delivered at 4 in-person visits (enrollment, 4, 8, and 12 months), and will consist of evidence-based material on diet, exercise, smoking, sexually transmitted infections, and cancer prevention. As recommended by the design teams, control participants will have access to a wide range of educational materials about healthy living, but will not receive additional counseling from the prevention nurse outside of the 4 in-person visits.

All participants in both intervention and education control arms will complete the following study assessments: 1) in-office BP obtained by a trained research assistant blinded to study group using a standardized protocol¹² (0, 4, 8, 12 months); 2) lipid profile (0, 4, 8, 12 months); 3) perceived ASCVD risk survey⁵⁶ (0, 12 months); 4) provider trust and communication survey (0, 12 months). Study visits will be calculated from the date of the baseline enrollment visit in months. Per protocol, study visits must be completed +/- 14 days from the calculated visit date.

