2. Nurse-managed medication protocols and adherence support. Participants with BP or non-HDL above goal will receive tailored medication management and adherence support. Algorithm-based care to reduce practice variation and clinical inertia has long been recommended to assure that patients are not “stuck” at sub-therapeutic doses of medications⁸². A meta-analysis of nurse and pharmacist-led cholesterol medication adherence interventions showed substantial improvements in adherence and 15-20mg/dL reductions in total cholesterol⁴². By using algorithms and clear decision rules to guide medication titration, the prevention nurse will make recommendations to providers to improve care by reducing clinical inertia, reducing variation, and allowing non-physician staff members to assist in care. A clear and complete algorithm will also help simplify the medical regimen and emphasize medications that are affordable, effective, and have low side-effect profiles.

[figure not shown]
At each visit (in-person or telephone) where recent home BP values (average weekly BP based on a minimum of three values) exceed 130/90mmHg (in line with 2017 ACC/AHA hypertension guidelines), the prevention nurse will review the medication list with the patient, including any recent medication regimen changes and potential side-effects of each medication⁸³. The nurse will provide counseling in several areas, including ways to enhance medication adherence and prevent or ameliorate side effects. For example, patients may be given a personalized medication schedule that shows when they should take their medications.

The prevention nurse will use the algorithms described below to decide on appropriate recommendations for medication changes and will approach the designated responsible provider (HIV, PCP, or non-HIV specialist) for prescriptions and lab orders. *The responsible provider will ultimately decide on final management decisions and may request to have the participant be taken OFF management protocols as clinically indicated (e.g. recent ASCVD events or advanced CKD), in which case the participant would continue all other components of the EXTRA-CVD intervention.*

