The primary outcome will be systolic BP at 12 months and secondary outcome will be non-HDL cholesterol at 12 months, both measured at 4 time-points (0, 4, 8, and 12 months). All BPs used for outcomes will be obtained by a blinded research assistant and cholesterol levels will be measured by lab personnel who are also blinded to treatment group. Because the outcomes are continuous, linear mixed-effects models⁸⁹ (LMM) will be used to examine the differences over time between the study arms. LMM will allow us to implicitly account for the correlation between a patient's repeated measurements over time. The general mean structure of the LMM we will use to examine the hypotheses is, $Y_{ij} = \beta_0 + \beta_1 * I(month = 4) + \beta_2 * I(month = 8) + \beta_3 * I(month = 12) + \beta_5 * arm * I(month = 4) + \beta_6 * arm * I(month = 8) + \beta_7 * arm * I(month12)$, where Y_{ij} represents the outcome of interest (i.e., SBP or non-HDL) for patient i at time j . In this model, we fit a common intercept and arm is the intervention group indicator. Similarly, time is classified, where for example, $I(month = 12)$ is a dummy variable equal to 1 for the 12 month time point. Random intercepts will be included for

each individual to account for correlation among repeated measurements over time. The primary analytic model will adjust for clinic site. The mixed effects model parameters will be estimated and tested using SAS PROC MIXED (SAS Institute, Cary, NC), and the hypothesis of between-arm differences over time will be tested using estimate statements within PROC MIXED. In particular, β_7 , the estimated difference in outcome between arms at 12 months, will be the primary effectiveness outcome assessed.

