For the tertiary outcome of cascade category, we will calculate an ordinal four-level variable at baseline, 4, 8, and 12 months. We will use a proportional odds model fit via generalized estimating equations to examine differences over time between study arms. The proportional odds assumption will be assessed using score tests, and the model will be relaxed to partial proportional odds if necessary. Robust sandwich standard errors will be used to account for potential overdispersion and correlation among the repeated observations over time. Similarly to the primary analysis, the model will adjust for clinic site and include the same general mean model specification. The primary hypothesis will be tested via SAS PROC GENMOD to assess whether the estimated proportions in each level at 12 months differ between arms. All analyses will be conducted following an intention to treat (ITT) principle.

Missing Data:

We will assess mechanisms for missing data in this study. LMM, implicitly accommodates missingness when the response is Missing At Random (MAR); that is, when missingness is due either to treatment, to prior outcome, or to other baseline covariates included in the LMM. We will address missing data by imputing missing values using multiple imputation procedures as described by Schafer. Once missing values have been imputed, each multiply-imputed data set can be analyzed using the LMM. Final parameter estimates and their standard errors will be calculated using Rubin's formula. We will analyze our data and report final study results with and without employing the multiple imputation strategy (compared to complete case analysis) and carefully examine and describe any discrepancies found.

Power:

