The power calculation for this study was based on our prior nurse-led BP intervention¹², a meta-analysis of cholesterol medication adherence interventions⁴², and baseline blood pressure and cholesterol data from our clinic sites. Power estimates were derived empirically via simulation in SAS 9.4. Simulated data were generated based on estimates from prior studies, such that we assumed a mean SBP at baseline of 145mmHg for both arms, with a reduction in the education control arm of 1mmHg by 12 months. For the intervention arm, we evaluated effect sizes (differences from education control at 12 months) of 5-7mmHg. We estimate that 15% of patients may drop out by the 12-month time point, and incorporated missing values into the simulated data based on a uniform pattern of 5% missing at 4 months, 10% at 8 months, and 15% at 12 months. The drop-out rate is consistent with prior interventional studies at our sites (80-88% retention at 12 months).^{11,12,90} We conservatively estimated variance components assuming a total standard deviation of 17 and a within-individual correlation of 0.4 among repeated SBP measurements. Similarly, for the secondary non-HDL outcome, we assumed a baseline value of 132mg/dL with a standard deviation of 41 and a within-individual correlation of 0.7, and evaluated sample size needed over effect sizes ranging from 10-20mg/dL.

After generating 1,000 simulated datasets under these assumptions, we fit the LMMs described above to each and assessed the effect of interest using two-sided tests with a type I

error rate of 0.05. Based on results, we will have >80% power to detect a 6mmHg lower systolic BP and >90% power to detect a 15mg/dL lower non-HDL cholesterol in the intervention arm vs. education control. Table 5 displays the sample sizes needed to detect a range of plausible *clinically significant* BP and non-HDL effects. A 6 mmHg improvement in systolic BP is associated with a ~20% decrease in ASCVD events⁹¹, and a 15mg/dL improvement in cholesterol is associated with ~10% decrease in clinical ASCVD events³¹.

Table 5: Sample size estimates to detect a range of plausible and clinically significant effect sizes						
	BP Effect Size			Non-HDL Effect Size		
	5mmHg	6mmHg	7mmHg	10mg/dL	15mg/dL	20mg/dL
70% Power	278	190	140	248	110	64
80% Power	350	234	178	310	148	80
90% Power	466	340	232	424	184	104

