133 variables will be reported as N (%). These statistics will be reported for the overall sample and by study
 134 arm. (Table 1)

135

136 **Primary analyses**

137 The primary intervention effect analyses will utilize continuous, linear mixed models (LMM) to test for
 138 differences over time between the study arms. The general mean structure of the LMM we will use to
 139 examine the hypotheses is:

$$140 \quad Y_{ij} = \beta_0 + \beta_1 I(\text{month}=4) + \beta_2 I(\text{month}=8) + \beta_3 I(\text{month}=12) + \\
 141 \quad \beta_5 \text{arm} * I(\text{month}=4) + \beta_6 \text{arm} * I(\text{month}=8) + \beta_7 \text{arm} * I(\text{month}=12) + \beta_8 \text{clinic2} + \\
 142 \quad \beta_9 \text{clinic3}$$

143

144 where Y_{ij} represents the outcome of interest (i.e., SBP or non-HDL) for patient i at time j . In
 145 this model, we fit a common intercept and arm is the intervention group indicator. Similarly, time is
 146 classified, where for example, $I(\text{month}=12)$ is a dummy variable equal to 1 for the 12 month time point.
 147 Random intercepts will be included for each individual to account for correlation among repeated
 148 measurements over time. The primary analytic model will adjust for clinic site as fixed effects,
 149 represented with indicator variables clinic2 and clinic3, above. The mixed effects model parameters will
 150 be estimated and tested using SAS PROC MIXED (SAS Institute, Cary, NC), and the hypothesis of
 151 between-arm differences over time will be tested using estimate statements within PROC MIXED. In
 152 particular, β_7 , the estimated difference in outcome between arms at 12 months, will be the primary
 153 effectiveness outcome assessed.

154

155 For the tertiary outcome of cascade category, we will calculate an ordinal four-level variable at baseline,
 156 4, 8, and 12 months. We will use a proportional odds model fit via generalized estimating equations to
 157 examine differences over time between study arms. The proportional odds assumption will be assessed
 158 using score tests, and the model will be relaxed to partial proportional odds if necessary. Robust sandwich
 159 standard errors will be used to account for potential overdispersion and correlation among the repeated
 160 observations over time. Similarly to the primary analysis, the model will adjust for clinic site and include
 161 the same general mean model specification. The primary hypothesis will be tested via SAS PROC

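### The SBP and non-HDL models name only a random intercept. Pre-specifying an unstructured covariance or sandwich standard errors would cheaply protect the 12-month standard error if variances or correlations differ between visits

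*Combined protocol and SAP*

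**What the plan says.** The protocol (Statistical Considerations) and the SAP (Primary analyses) describe the same model for SBP and non-HDL. It has a common intercept, visit indicators, arm-by-visit terms and clinic site, fitted in SAS PROC MIXED. The month-12 arm difference, β7, is the effect of interest. On correlation, the SAP says only "Random intercepts will be included for each individual to account for correlation among repeated" measurements over time, and the protocol has the same sentence: "each individual to account for correlation among repeated measurements over time". Neither document names a residual covariance structure, a standard-error option, a degrees-of-freedom method or a fallback for this model.

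The tertiary cascade outcome is treated differently: "Robust sandwich standard errors will be used to account for potential overdispersion and correlation among the repeated observations over time". The multiple-imputation run in the protocol's Missing Data section goes back to the same mixed model ("each multiply-imputed data set can be analyzed using the LMM").

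The Power section uses one SD and one correlation per outcome: a total SD of 17 with "a within-individual correlation of 0.4 among repeated SBP measurements", and for non-HDL "a standard deviation of 41 and a within-individual correlation of 0.7".

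**The concern.** A random intercept with PROC MIXED defaults gives compound symmetry: the same variance at every visit and the same correlation for every pair of visits. Baseline means are constrained equal, so the precision of β7 depends mainly on the month-12 variance and the baseline-to-month-12 correlation. The model replaces both with values pooled over all visits. If either differs from its pooled value, and the two differences do not offset, the standard error, confidence interval and p-value for β7 are miscalibrated.

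The design offers one reason why spread might change in one arm. Under the nurse-managed protocols, "Participants with BP or non-HDL above goal will receive tailored medication management and adherence support", and this applies to the intervention arm. Controls receive education and "will not receive additional counseling from the prevention nurse outside of the 4 in-person visits". Lowering mainly the high values can change the SD in one arm. SAP Table 2 will show SDs by arm and visit, but no rule says what follows if they differ, and the correlations are not reported. A change of covariance model made after seeing the data would be post hoc.

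**Working it through.** **Inputs (protocol, Power and Aim 2 sections).** n=300, 1:1; missing 5%, 10% and 15% at months 4, 8 and 12; two-sided 0.05; SBP SD 17, ρ 0.4; non-HDL SD 41, ρ 0.7.

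**Step 1: reproduce the plan.** With a common baseline mean, SE(β7) ≈ √[2σ²(1−ρ²)/m], where m = 150 × 0.85 = 127.5 per arm.
- SBP: √(2 × 289 × 0.84 / 127.5) = √3.808 = 1.95. The full calculation, which also uses months 4 and 8, gives 1.94.
- Non-HDL: √(2 × 1681 × 0.51 / 127.5) = √13.448 = 3.67. The full calculation gives 3.63.
- Power: Φ(6/1.94 − 1.96) = 87% and Φ(15/3.63 − 1.96) = 98.5%. These agree with the stated >80% and >90%.

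**Step 2: how a departure acts.** Write r for the pooled correlation and ρ₀₁₂ for the true baseline-to-month-12 correlation. With equal SDs, the model reports a variance proportional to 1 − r², while the true variance is proportional to 1 − 2rρ₀₁₂ + r². The actual error is 2Φ(−1.96 × reported SE / true SE). Correlations below are for visits one, two and three intervals apart, so the six pairs of visits have weights 3, 2 and 1.
- SBP 0.45/0.40/0.35: r = (3×0.45 + 2×0.40 + 0.35)/6 = 0.4167. Ratio = √(0.8264/0.8819) = 0.968, so error = 2Φ(−1.897) = 5.8%.
- Non-HDL 0.75/0.70/0.65: r = 4.30/6 = 0.7167. Ratio = √(0.4864/0.5819) = 0.914, so error = 2Φ(−1.792) = 7.3%.
- Non-HDL 0.8/0.7/0.6: r = 4.40/6 = 0.7333. Ratio = √(0.4622/0.6578) = 0.838, so error = 2Φ(−1.643) = 10.0%. The full calculation gives 10.1%.

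**Step 3: full large-sample results for the random intercept (nominal 5%).** Every departure is assumed.

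| Outcome and departure | Actual error |
|---|---|
| SBP, planning case | 5.0% |
| SBP, intervention-arm SD 17-16-16-15 | 4.3% |
| SBP, intervention-arm SD 17-15-15-15 | 4.6% |
| SBP, intervention-arm SD 17-18-18-19 | 5.7% |
| SBP, 0.45/0.40/0.35 | 5.8% |
| SBP, same decay with intervention-arm SD 17-16-16-15 | 5.1% |
| Non-HDL, planning case | 5.0% |
| Non-HDL, intervention-arm SD 41-39-39-37 | 4.5% |
| Non-HDL, intervention-arm SD 41-43-43-45 | 5.6% |
| Non-HDL, 0.72/0.70/0.67 | 6.1% |
| Non-HDL, 0.75/0.70/0.65 | 7.3% |
| Non-HDL, same decay with intervention-arm SD 41-39-39-37 | 6.8% |
| Non-HDL, 0.8/0.7/0.6 | 10.1% |

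The unstructured model gives 5.0% in each row, with equal dropout in the two arms. In interval terms, the reported 95% half-width is 3.77 against a correct 3.89 mmHg (SBP 0.45/0.40/0.35), and 6.93 against 7.58 mg/dL (non-HDL 0.75/0.70/0.65).

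A direct model of treating the excess above goal in the intervention arm was scaled to the planned effects. Confidence-interval non-coverage was 4.34% to 5.32% for SBP and 4.15% to 6.04% for non-HDL.

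**Step 4: do the alternatives work?** Simulation, 20,000 trials per scenario, Monte Carlo SE about 0.15 points (0.2 for the 10% case):

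| Scenario | Random intercept | With EMPIRICAL | Unstructured, KR |
|---|---|---|---|
| SBP, exchangeable | 4.9% | 5.1% | 4.9% |
| SBP, intervention-arm SD 17-16-16-15 | 4.5% | 5.3% | 5.1% |
| SBP, 0.45/0.40/0.35 | 5.4% | 4.8% | 4.7% |
| Non-HDL, exchangeable | 5.0% | 5.2% | 5.0% |
| Non-HDL, 0.75/0.70/0.65 | 7.7% | 5.5% | 5.2% |
| Non-HDL, 0.8/0.7/0.6 | 10.2% | 5.1% | 4.8% |

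**Step 5: cost of the unstructured model when exchangeability holds.** It estimates 4×5/2 = 10 covariance parameters instead of 2. The variance ratio for β7 was 1.004 at n=300, 1.013 at n=102 and 1.028 at n=48. Without a degrees-of-freedom correction, error at n=48 was 7.0% against 5.6% for the random intercept.

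**The case against.** The plan pre-specifies a complete, conventional model that matches its own planning inputs. The one mechanism that can be drawn from the documents, treating values above goal, moves SBP error only to about 4.3% to 5.3%, on both sides of nominal. The clearly liberal figures concern the secondary outcome and need a decay in correlation for which the documents give no figure. A falling SD can partly cancel that decay. The compound-symmetry reading is also an inference, since the text does not rule out a further residual structure. All of this stands, and it limits the point to an improvement.

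It is also fair that the unstructured model is not the only remedy. Sandwich standard errors on the stated model did nearly as well in the simulations, so either is acceptable.

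Three stronger readings are tempting and are not supported:
- **The primary test is invalid or liberal as planned.** No visit-specific SD or correlation is given, and the direction of any error cannot be known in advance.
- **The unstructured model is free and always valid.** It needs a degrees-of-freedom method and a fallback, and it costs more in small strata. With arm-specific SDs and unequal dropout (10% against 20% assumed), the arm-pooled version gives about 5.1% to 5.2%.
- **The power statement is wrong.** It reproduces under the plan's own assumptions.

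**Conclusion.** This is a worthwhile, inexpensive improvement, and not the correction of a demonstrated error. If compound symmetry holds, nothing material changes. If it fails, the month-12 inference can be mildly off for SBP in either direction (about 4.3% to 5.8% for the mild departures tried). For non-HDL it can be more clearly liberal if the correlation decays: about 6% to 7% for mild decay and 10% for 0.8/0.7/0.6.

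These figures rest on the PROC MIXED default reading, a correct mean model, the planned n and dropout, and dropout unrelated to the readings. They do not separate the two remedies when dropout depends on earlier values.

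**What to change.** Keep the mean model. In the SAP's Primary analyses section, pre-specify one of the following for SBP, non-HDL and the exploratory lipids:
- an unstructured within-participant covariance over the four visits (REPEATED visit / SUBJECT=id TYPE=UN) with DDFM=KR, and the random intercept with the EMPIRICAL option as the named fallback if it does not converge; or
- the stated random intercept with EMPIRICAL standard errors throughout.

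Use the same choice in the protocol's multiple-imputation run.

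The cost is one sentence and no new data. In simulation under compound symmetry, the mean SE was 1.944 (unstructured, KR) against 1.941 (random intercept) for SBP, and 3.634 against 3.626 for non-HDL. The subgroup models mirror the primary one, and the treating-physician analysis repeats it in strata whose size is not given. The SAP should therefore allow the fallback there. Neither Kenward-Roger nor EMPIRICAL was tested in strata that small.

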PLHIV are known to have a 1.5-2x higher risk of atherosclerotic cardiovascular disease (ASCVD) compared to uninfected individuals, a risk that persists despite viral suppression on ART. Thus, once PLHIV achieve the final step of the HIV treatment cascade, providers have an important opportunity to focus on preventing ASCVD and other non-AIDS comorbidities. We envision extending the treatment cascade for high blood pressure (BP) and high cholesterol, which account for much of the population-level ASCVD risk in PLHIV, as follows: Step 1, appropriate screening and diagnosis; Step 2, appropriate treatment; and Step 3, achievement of guideline-based treatment targets. Currently, PLHIV are sub-optimally treated for high BP and cholesterol, possibly due to low perceived risk for ASCVD or challenges in primary care coordination between HIV specialists and non-HIV providers. Non-physician led approaches may address these barriers.

Our overarching goal is to improve the BP and cholesterol treatment cascade for PLHIV on suppressive ART to reduce ASCVD risk. Guided by a RE-AIM framework (Reach x Efficacy—Adoption, Implementation, Maintenance), and using a mixed-methods clinical effectiveness trial design, our experienced multi-disciplinary team will test a contextually adapted ASCVD prevention nurse-led intervention (EXTRA-CVD) to reach guideline-based BP and cholesterol targets. The study will be conducted in three racially and ethnically diverse clinic contexts that are broadly representative of HIV specialty care in the US.

Aims

Aim 1: Conduct a baseline assessment of ASCVD preventive care and perceptions of ASCVD risk in the HIV specialty clinic environment.

Sub-Aim 1.1: Adapt the EXTRA-CVD intervention components to the HIV specialty clinic context with key stakeholder input and data from the baseline assessments

***Aim 2:* Evaluate the 12-month efficacy of the EXTRA-CVD intervention to improve BP and cholesterol control in PLHIV (Aim 2)**

Aim 3: Conduct a process evaluation of the EXTRA-CVD intervention (Aim 3)

Hypothesis

We hypothesize that our prevention nurse-led intervention will lead to a clinically significant 6mmHg reduction in systolic BP and 15mg/dL reduction in non-HDL cholesterol over 12 months compared to those receiving general prevention education only.

44 **Study Design**

45 Two-arm parallel randomized controlled clinical trial

46 **Data Source**

47 Primary data collection with trial participants.

- 48 • Vitals:

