- 91 • Pregnant, breast-feeding, or planning a pregnancy during the study period
- 92 • Planning to move out of the area in the next 12 months
- 93 • Non-English Speaking

94 **Outcomes**

- 95 • **Primary:** 12-month change in systolic BP, calculated as the mean of two systolic BP readings
- 96 measured in the right arm, 1 minute apart.
- 97 • **Secondary:** 12-month change in non-HDL cholesterol, calculated as total cholesterol – HDL.
- 98 • **Tertiary:** change in the extended cascade categories for hypertension and hypercholesterolemia
- 99 ○ *Hypertension: 4-level category*
 - 100 ▪ Undiagnosed: hypertension is not listed on the EMR problem list
 - 101 ▪ Appropriately diagnosed: hypertension listed on the EMR problem list
 - 102 ▪ Appropriately managed: at least one medication prescribed for hypertension
 - 103 ▪ At treatment goal: <130 systolic
- 104 ○ *Hypercholesterolemia: 4-level category*
 - 105 ▪ Undiagnosed: hypercholesterolemia is not listed on the EMR problem list
 - 106 ▪ Appropriately diagnosed: hypercholesterolemia listed on the EMR problem list
 - 107 ▪ Appropriately managed: at least one medication prescribed for
 - 108 hypercholesterolemia
 - 109 ▪ At treatment goal, based on lifetime ASCVD risk
 - 110 - Low-moderate risk: <130 mg/dl
 - 111 - High: <100 mg/dl
 - 112 - Very high: <100 mg/dl
- 113 ○ Measured at each time point
 - 114 ▪ Diagnosis, management: EMR review by nurse
 - 115 ▪ At goal: measurement at that visit
- 116
- 117 • **Exploratory:** change in additional lipid measurements
 - 118 ○ Total cholesterol
 - 119 ○ Triglycerides
 - 120 ○ HDL
 - 121 ○ LDL
- 122

123 **Statistical Analysis**

124 ***Descriptive analyses***

125 Beginning with the chart review process, we will track ineligibility (number of patients, reasons),
126 declining to participate, and agreeing to participate but not proceeding to the initial visit. Once a patient
127 agrees to the phone screen, we will collect age, race, ethnicity, sex at birth, and gender. We will compare
128 demographics for those who enroll in the study to those who decline participation and to those who are
129 not eligible, using two sample t-tests (or nonparametric equivalent) and χ^2 tests. (*Table S1*)

130
131 We will further describe participating patients' characteristics (sociodemographic, lifestyle, medical
132 history). Continuous variables will be reported using mean (SD) or median (Q1, Q3) and categorical

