 162 GENMOD to assess whether the estimated proportions in each level at 12 months differ between arms.

163

164 All analyses will be conducted following an intention to treat (ITT) principle using all available data.
 165 Clinically significant changes specified *a priori* are a 5-point change for SBP and a 15-point change for
 166 non-HDL cholesterol.

167

168 **Missing data**

169 We will assess mechanisms for missing data in this study. LMM, implicitly accommodates missingness
 170 when the response is Missing At Random (MAR); that is, when missingness is due either to treatment, to
 171 prior outcome, or to other baseline covariates included in the LMM.

172

173 Our primary analysis will include all available study-collected data. Those with missing SBP or non-HDL
 174 cholesterol will remain missing for the corresponding cascade, even if EMR data is available for the first
 175 two categories (because it would be missing for the last categories).

176

177 **Attrition bias**

178 As part of our examination of missing data, we will assess differences in baseline characteristics (e.g.,
 179 clinic site, demographics, clinical values, medical history) by retention at each follow up time point. We

180 will use two sample t-tests (or Wilcoxon rank sum tests) for continuous variables and χ^2 tests for
181 categorical variables.

182

183 ***Subgroup analyses and moderation***

184 Pre-specified sub-group analyses of the primary, secondary, and tertiary outcomes will include clinic site,
185 sex, and baseline ASCVD risk (<20% 10-year risk vs. >20% or prior ASCVD). For each category, we
186 will examine the interactions with intervention arm and time. Generally, the modeling approach will
187 mirror that described above for each outcome. Three separate analyses for each outcome will be
188 conducted to assess the effect of each potential moderator. Models will be fit in SAS PROC MIXED and
189 GENMOD, as described above, and the moderating effect of each of the three factors will be assessed via
190 the hypothesis test of the three-way interactions among subgroup, treatment, and time points (4, 8, and 12
191 months). As these analyses are exploratory and hypothesis generating in nature, we will not adjust the
192 alpha value. Interpretation will focus on trends and consistent results over time.

193 Given that some of the participants are treated by study investigator physicians, we will conduct an

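### Does the SAP's 5-point clinically significant SBP change conflict with, or leave undefined, the 6 mmHg in its hypothesis?

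*Combined protocol and SAP*

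**What the plan says.** The SAP gives an SBP figure in two places. Its Hypothesis section expects a "clinically significant 6mmHg reduction in systolic BP and 15mg/dL reduction in non-HDL cholesterol over 12 months compared to those receiving general prevention education only". The last paragraph of Primary analyses then states that the clinically significant changes set beforehand "are a 5-point change for SBP and a 15-point change for" non-HDL cholesterol. That sentence names no comparator, time point or use.

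The Outcomes section lists the primary outcome as "12-month change in systolic BP, calculated as the mean of two systolic BP readings" from the right arm. The Primary analyses section models the SBP level at each visit and singles out β7: "the estimated difference in outcome between arms at 12 months, will be the primary" effectiveness outcome. SAP Table 3 reports continuous effects as β with a 95% confidence interval at 4, 8 and 12 months.

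The protocol's Power section says that "we evaluated effect sizes (differences from education control at 12 months) of 5-7mmHg", and the sample-size table there (Table 5) describes that range as plausible and clinically significant. The power statement is tied to the middle value: "we will have >80% power to detect a 6mmHg lower systolic BP". So is the clinical rationale: "A 6 mmHg improvement in systolic BP is associated with a ~20% decrease in ASCVD events".

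**The concern.** A threshold set in advance is meant to fix the clinical reading of a result before anyone sees it. Here the same SAP calls two different SBP values clinically significant, 5 and 6, while the non-HDL values agree (15 and 15). The word change also names the primary outcome, where it sounds like something measured in each patient. A reader could therefore ask whether 5 is meant for the arm difference or for individual falls, and whether an estimate of, say, 5.5 mmHg meets the plan or falls short of it. If 5 is the between-arm value that matters, a further question is whether 300 participants are enough to detect it.

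At stake is only the label attached to the result. The test of β7, the two-sided 5% level, the sample size and the stated power do not depend on it.

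**Working it through.** **Step 1. Which comparison does the 5 refer to?** Four features of the text point to the arm difference.

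- Location: the sentence closes the Primary analyses section, which has already named the 12-month arm difference as the primary effectiveness parameter.
- Outcome modelled: the mixed model uses the SBP level at each visit. No change score is computed per patient, and the outcome list contains no responder endpoint.
- The paired value: the 15 for non-HDL in this sentence equals the 15 mg/dL in the hypothesis, which is stated relative to education control.
- The protocol: 5 mmHg is the lower end of a range defined as differences from control at 12 months.

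**Step 2. Do 5 and 6 contradict each other?** Not on that reading. A trial may regard 5 as worth having and be designed around 6. The protocol's sample-size table includes both among its clinically significant effects.

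**Step 3. Reproduce the protocol's sample-size table.** Inputs from the Power section: SD 17, within-person correlation 0.4, 5/10/15% missing at 4/8/12 months, two-sided 0.05. Allocation is 1:1 and n=300, so 150 per arm. The calculation uses the stated model (common baseline, random intercept), monotone dropout and no site terms.

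| SBP effect | Power | Protocol N | Recalculated N |
|---|---|---|---|
| 5 mmHg | 70% | 278 | 279 |
| 5 mmHg | 80% | 350 | 355 |
| 5 mmHg | 90% | 466 | 475 |
| 6 mmHg | 70% | 190 | 194 |
| 6 mmHg | 80% | 234 | 246 |
| 6 mmHg | 90% | 340 | 330 |

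The largest gap is 234 against 246. Recalculated power at 234 is 78%. The protocol used 1,000 simulated datasets, so the Monte Carlo standard error near 80% is √(0.8 × 0.2 / 1000) = 1.3 percentage points, and a 2-point gap is unremarkable.

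**Step 4. Standard error of β7 at n=300.** The model gives 1.94 mmHg. A hand check that adjusts for baseline only and uses the 85% with 12-month data: 17 × √(1 − 0.4²) = 15.58; 0.85 × 150 = 127.5 per arm; 15.58 × √(2/127.5) = 1.95.

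**Step 5. Power at each figure.** Power = Φ(effect/SE − 1.96).

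- At 5 mmHg: Φ(5/1.94 − 1.96) = Φ(0.62) = 73%. Interpolating the protocol's table gives the same: 70 + 10 × (300 − 278)/(350 − 278) = 73%.
- At 6 mmHg: Φ(6/1.94 − 1.96) = Φ(1.13) = 87%, consistent with the claim of more than 80%.

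A 4,000-replicate simulation gave 74% and 87%.

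**Step 6. How often would the two figures give different labels?** If the true effect is 6 mmHg, the estimate reaches 5 with probability Φ((6 − 5)/1.94) = Φ(0.515) = 70%, and reaches 6 with probability 50%. It lands between them about 70 − 50 = 20% of the time. The smallest significant difference is 1.96 × 1.94 = 3.8 mmHg, so any estimate between 5 and 6 would be significant at this standard error, whichever label is attached.

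**The case for a change.** The best argument for acting is that the between-arm reading is inferred, not written. The SAP does not cite the protocol's effect range. If 5 had been taken as the bottom of that range, the matching non-HDL value would be 10, the lowest effect in the protocol's table, yet the SAP uses 15. The protocol gives an event-reduction rationale for 6 mmHg and none for 5. Nor does the SAP say whether the point estimate or a confidence limit is to be compared with 5. One sentence would settle all of this at almost no cost.

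Much of this is fair as description: the definition is missing and the choice of 5 is unexplained. It does not go further. The non-HDL comparison shows only that 15 was not picked as the bottom of its range; it lends nothing to a within-patient reading, which would need a responder analysis that the SAP does not contain. The estimate-or-limit question would matter if some rule turned the threshold into a verdict, and there is none. The 6 mmHg is a hypothesised effect, not a bar that the estimate must clear.

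**Conclusion.** No change to the plan follows. This is missing detail that an analyst would fill sensibly: 5 mmHg and 15 mg/dL are reference values for interpreting β7 at 12 months, and 6 mmHg is the effect the trial was designed around. The two SBP figures are compatible, and nothing computed in the trial depends on the 5.

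The practical size is about a 20% chance, at a true effect of 6 mmHg, of an estimate that reaches 5 but not 6. In that case the report still gives the same estimate, interval and p-value. Power for a true 5 mmHg difference is about 73%, below 80%, but the protocol's own table already shows this (350 participants for 80%) and the plan claims its power only at 6 mmHg.

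These figures rest on the protocol's SD, correlation and dropout, with monotone missingness, normal errors and no site adjustment. The reading of the 5 as a between-arm value rests on context, since the SAP does not state it. If the authors revise the SAP for another reason, they could state which comparison the 5 and 15 describe, but the analysis does not need it.
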